**[name] and [name]**

**Pablo Tobon Uribe Hospital**

**NCT: 2017.019**

**Date: Aug 18 / 2020**

## 1 JUSTIFICATION

Hemothorax is a common emergency and is commonly the result of trauma, both blunt and penetrating. Although closed drainage thoracostomy is commonly adequate for the initial management of a hemothorax in most cases, failure of closed thoracostomy and formation of the coagulated hemothorax can occur in up to 5 to 30% of cases.

Therefore, we want to impact through a simple and low-cost procedure such as traumatic hemothorax aspiration in the adult population, prior to insertion and fixation of the thoracostomy tube to evacuate all the hemothorax, thus reducing the formation of clots in these patients and the probability of coagulated hemothorax, therefore acting early on the incidence of this complication so ominous for the prognosis and follow-up in the evolution of the patient

### 1.1 Problem to intervene

Generation of post-traumatic clotted hemothorax, that usually requires surgical intervention for the evacuation of the hemothorax and pulmonary decortication to resolve lung entrapment.

## **1.2 HYPOTHESIS**

### 1.2.1 Null:

Adult patients who come to the emergency department with post-traumatic hemothorax have no benefit in reducing the incidence of coagulated hemothorax and / or empiema with aspiration of the hemothorax with Yankauer cannula, prior to insertion of the tube into the chest for closed drainage

### 1.2.2 Alternating:

Adult patients who come to the emergency department benefit from aspiration of the hemothorax with a Yankauer cannula, prior to insertion of the tube into the chest for closed drainage, in reducing the incidence of coagulated hemothorax and / or empyema

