## 2 OBJECTIVES

### 2.1 General:

Reduce the incidence of post-traumatic clotted hemothorax in the adult population admitted to the emergency department with traumatic hemothorax, by aspiration with a Yankauer cannula through the insertion hole of the thoracostomy tube prior to its introduction by the surgeon.

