### 2.2 Specific:

- Evidence other complications other than coagulated hemothorax, related to closed thoracostomy
- To determine the specific complications of the operated group in relation to aspiration under sedation of the pleural space
- Microbiological analysis of coagulated hemothorax in the population included in the study that presents this complication

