### **3.6 Sampling and type of sampling**

Taking into account local statistics on the incidence of coagulated hemothorax of 16.7%, with the intention of reducing it to 5%, we need a sample of 125 patients in each arm, that is, approximately 250 patients in total, calculating a loss of patients of 15% in each arm. According to statistical data from the Pablo Tobon Uribe Hospital, in 2015, 148 patients underwent closed thoracostomy, for which a total patient collection time of approximately 20 months is calculated.

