## **3.9 Data analysis**

The form data will be entered in a database of the SPSS program. Analysis of each separate group will be performed and then a comparison based on days of hospitalization, percentage of hemothorax retained, empyema, need for surgery, postoperative pain, reoperation or readmission. Chi2 test to establish statistical significance of these differences, with a bivariate analysis

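### The hypotheses let benefit be claimed on clotted hemothorax, empyema or both, but the objective and sample size use clotted hemothorax alone and section 3.9 labels no primary outcome.

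*Combined protocol and SAP*

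**What the plan says.** All references are to the combined protocol and SAP.

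- **1.2.1 and 1.2.2 (hypotheses).** Under the null, patients "have no benefit in reducing the incidence of coagulated hemothorax and / or empiema". The alternative claims benefit "in reducing the incidence of coagulated hemothorax and / or empyema".
- **1.1 (problem).** The target is "Generation of post-traumatic clotted hemothorax". Empyema is not mentioned.
- **2.1 (general objective).** "Reduce the incidence of post-traumatic clotted hemothorax in the adult population". Again, no empyema.
- **2.2 (specific objectives).** "Evidence other complications other than coagulated hemothorax, related to closed thoracostomy". On a natural reading, empyema belongs here.
- **3.6 (sample size).** The calculation rests on "local statistics on the incidence of coagulated hemothorax of 16.7%, with the intention of reducing it to 5" per cent, giving 125 per arm with 15% loss.
- **3.9 (analysis).** The groups are compared on "comparison based on days of hospitalization, percentage of hemothorax retained, empyema, need for surgery, postoperative pain, reoperation or readmission", followed by "Chi2 test to establish statistical significance of these differences, with a bivariate analysis".

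No outcome is called primary anywhere, and no composite is defined. Alpha, sidedness, power and the expected empyema rate are not stated.

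**The concern.** The hypothesis says what the trial may conclude, and it is the one place that differs from the objective and the sizing. Its wording admits three success rules: fewer clots, fewer empyemas, or fewer patients with either. Section 3.9 does not choose between them.

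Two things are at stake. The same data can be significant under one rule and not under another. And if the rule is chosen after the results are seen, the false-positive rate can exceed that of a single test. In addition, the sample size supports only the clot comparison, so the power of the other two is unplanned.

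**Working it through.** **Inputs from the plan.** Clotted hemothorax 16.7% in controls and 5% with aspiration; 125 per arm; 15% loss (all 3.6); chi-square test (3.9).

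**Assumptions, none of them in the documents.** Two-sided 0.05; 80% power for the sample size; 125 × 0.85 = 106 evaluable per arm; empyema without clot (called e) in 0% to 5% of control patients; 0% or 20% of clot patients also having empyema, where empyema alone is tested.

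**Step 1: reproduce the plan's figure.** With unpooled variance,

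n = (1.960 + 0.842)² × [0.167 × 0.833 + 0.05 × 0.95] / (0.167 − 0.05)² = 7.849 × 0.1866 / 0.01369 = 107.

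107 / 0.85 = 126, against the stated 125. The clot rates alone explain the sample size; no empyema input is needed.

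**Step 2: power and disagreement.** Each patient falls in one of three classes: clot, empyema without clot, or neither. The composite rate is therefore the clot rate plus e. Each comparison uses the Pearson statistic z = (p₁ − p₂) / √(2p̄(1 − p̄)/n), with significance at |z| > 1.96. Enumerating all outcomes at 106 per arm, clot against placement of e, gives clot power of 81.4% and:

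| e in controls | Composite power, e unaffected by treatment | Trials where clot and composite disagree | Composite power, e falls by 5/16.7 | Trials where they disagree |
|---|---|---|---|---|
| 0% | 81.4% | 0% | 81.4% | 0% |
| 1% | 77.8% | 8.1% | 83.8% | 5.2% |
| 3% | 71.4% | 15.7% | 87.9% | 9.5% |
| 5% | 65.9% | 21.5% | 91.2% | 12.1% |

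If all 125 per arm are evaluable, clot power is 87%, composite power runs from 72% to 95%, and disagreement runs from 0% to 19%.

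**Step 3: false positives (clot 16.7% in both arms, 106 per arm).** The first column is by enumeration. The other two are by simulation of 400,000 trials per setting. The benefit-direction rate is in brackets; a single test has 2.5% in that direction.

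| e | Clot or composite | Clot, composite or empyema; no overlap | Same; 20% overlap |
|---|---|---|---|
| 0% | 5.0% (2.5%) | 5.1% (2.5%) | 8.8% (4.4%) |
| 1% | 6.2% (3.1%) | 7.6% (3.8%) | 9.8% (4.9%) |
| 3% | 7.0% (3.5%) | 10.8% (5.5%) | 10.9% (5.5%) |
| 5% | 7.5% (3.8%) | 11.1% (5.7%) | 11.6% (5.8%) |

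At e = 0 with no overlap there is no empyema at all, so the 5.1% is the single-test 5.0% with simulation error. With 125 evaluable per arm, the first column runs from 4.8% to 7.2%.

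**Step 4: empyema as the only outcome.** If its total control rate falls by the same ratio (5/16.7), exact power at 106 per arm is 1.6% at a control rate of 1%, 16.8% at 3% and 27.7% at 5%. The top of the overlap range implies a total of 0.20 × 16.7% + 5% = 8.3%, where power is about 47%.

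**The case against.** The best reply is that the plan already shows which outcome leads. The problem statement, the general objective and the sample size name clotted hemothorax and not empyema, and the specific objectives set other complications apart. Only the two hypothesis sentences stray. This stands, and it is the main reason to treat the point as a correction to make rather than a fatal fault. It does not remove the conflict: a structural hint is not a stated primary outcome, and the hypothesis still permits a different claim.

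Second, the harm may be nil. If every empyema occurs in a patient with a clot, clot and composite are the same event, and inflation and disagreement between them are both zero. The documents give no empyema rate that would rule this out. Even otherwise, choosing between clot and composite never takes the benefit-direction rate above 3.8%. This also stands. The larger figures need empyema alone to count as success, together with assumed rates and overlap.

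A reader might infer more than the text supports:

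- *That the sample size is wrong.* It is not shown to be. It reproduces for clot under conventional assumptions.
- *That all seven outcomes in 3.9 are routes to success*, counting reoperation and readmission as two. Seven independent tests would give 1 − 0.95⁷ = 30.2%, but the hypotheses name only clot and empyema.
- *That the retained-hemothorax percentage in 3.9 is a volume of blood and so a further endpoint.* The chi-square test and the patient-level incidence in 3.6 point to a share of patients. It is a minor matter of terminology.
- *That the rule was, or will be, chosen after seeing the data.* Nothing in the documents says so.

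**Conclusion.** The conflict is real and should be fixed before analysis. The hypotheses admit three success rules, the trial is sized for one, and 3.9 does not decide between them.

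Its size is conditional on the assumptions listed above. The two-sided false-positive rate is 5.0% to 7.5% for a choice between clot and composite, and 5.0% to about 11.6% if empyema alone may also carry the claim. In the benefit direction these are 2.5% to 3.8% and 2.5% to about 5.8%, against 2.5% for one test. Composite power is 66% to 91% against 81% for clot, and the two disagree on significance in 0% to about 21% of trials. Empyema alone would have about 2% to 28% power at a total control rate of 1% to 5%, or about 47% at 8.3%.

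The textual finding is certain. The numerical harm is nil to modest, because every empyema figure is assumed. A reading that the trial has no discernible main outcome, or that its error rate is seriously out of control, goes beyond the documents.

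**What to change.** In 1.2 and 3.9, name clotted hemothorax (yes or no for each patient, compared as proportions of patients) as the single primary outcome. Test it at one stated significance level, for example two-sided 0.05, which the documents do not give. Delete the reference to empyema from both hypotheses. Use the same outcome term in 3.9 in place of the retained-hemothorax percentage. Label empyema, the composite and the other 3.9 outcomes as secondary, reported with confidence intervals and without a confirmatory claim.

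Date the change before any comparison by arm. The document is dated August 2020 and describes randomization in the past tense, but does not say whether outcomes have been compared. If they have, disclose the choice as post hoc.

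The cost is a few wording changes, and the 125 per arm stands. The downside is that a significant result on empyema or the composite alone can no longer carry the conclusion.

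A composite primary outcome is a valid alternative, but it needs a stated control rate and a new sample size. By the Step 1 formula, with e from 1% to 5%, this is about 137 to 177 per arm if those cases are unaffected (116/0.85 and 150/0.85), or 118 down to 93 if they fall in proportion (100/0.85 and 79/0.85).

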## 2 OBJECTIVES

### 2.1 General:

Reduce the incidence of post-traumatic clotted hemothorax in the adult population admitted to the emergency department with traumatic hemothorax, by aspiration with a Yankauer cannula through the insertion hole of the thoracostomy tube prior to its introduction by the surgeon.

### 2.2 Specific:

- Evidence other complications other than coagulated hemothorax, related to closed thoracostomy
- To determine the specific complications of the operated group in relation to aspiration under sedation of the pleural space
- Microbiological analysis of coagulated hemothorax in the population included in the study that presents this complication

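### Procedural and sedation complications are sought for the operated group or left out of the comparison list, so harm outside the listed outcomes has no between-arm estimate

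*Combined protocol and SAP*

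**What the plan says.** Two of the three specific objectives in section 2.2 concern complications.

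- The first is "Evidence other complications other than coagulated hemothorax, related to closed thoracostomy". It has no arm restriction, and every eligible patient needs a closed thoracostomy (section 3.4).
- The second is "To determine the specific complications of the operated group in relation to aspiration under sedation of the pleural space". It refers to one arm.

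Section 3.9 analyses each group separately and then makes a "comparison based on days of hospitalization, percentage of hemothorax retained, empyema, need for surgery, postoperative pain, reoperation or readmission". The method is "Chi2 test to establish statistical significance of these differences, with a bivariate analysis".

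The list names no complication of sedation, of the aspiration or of tube placement. Empyema is the only item on it that could also fall under the first objective. The documents do not define these complications, grade them or set a period for observing them.

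**The concern.** By the hypotheses (1.2) and the general objective (2.1), aspiration is an extra step before the tube goes in, through the same opening. Patients in both arms have chest trauma and a tube. Bleeding, air leak or desaturation may come from the injury, the tube, the sedation or the aspiration, and in one patient the cause is often unclear. Only the control-arm rate shows how many such events would have happened anyway.

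If these events are summarised for the operated group alone, or recorded but never compared, the trial could report a benefit on clotted hemothorax with no randomised estimate of the procedural or sedation harm to set against it. The plan would also leave its first two objectives without a matching analysis.

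**Working it through.** **Step 1. Objectives against analysis.**

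| Item | Scope in 2.2 | Compared in 3.9? |
|---|---|---|
| Complications of aspiration under sedation | Operated group | No |
| Other complications of closed thoracostomy | Not limited to one arm | Only empyema |
| Retained hemothorax, surgery, pain, reoperation, readmission | Not set out as complications | Yes |

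The gap is rows one and two, less empyema.

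**Step 2. Number of patients available.** Section 3.6 says "we need a sample of 125 patients in each arm, that is, approximately 250 patients in total". The aim is a fall from 16.7% to 5%, and the figure allows for 15% loss per arm. It states neither alpha nor power. Assuming two-sided 5% and 80% power, with unpooled variance:

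n = (1.96 + 0.842)² × (0.167 × 0.833 + 0.05 × 0.95) / (0.167 − 0.05)² = 107 per arm after rounding up.

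Allowing for loss, 107 / 0.85 = 126, which reproduces the stated 125 to within one patient. The point does not depend on this figure. It fixes the range of evaluable patients: 125 per arm with no loss, or 125 × 0.85 = 106 with the full allowance. Events around the procedure would mostly be seen before patients are lost, so 125 may be nearer the mark for them.

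**Step 3. Precision of a two-arm comparison.** The documents give no complication rate, so the rates here are assumptions. With the same rate p in both arms, the 95% half-width of the risk difference is 1.96 × √(2p(1 − p)/n).

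| Assumed p | n = 106 | n = 125 |
|---|---|---|
| 5% | 5.9 points | 5.4 points |
| 10% | 8.1 points | 7.4 points |
| 15% | 9.6 points | 8.9 points |

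For example, at p = 10% and n = 106: 1.96 × √(0.18/106) = 0.081.

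**Step 4. What excess could be detected.** Two-sided 5%, 80% power, with power = Φ{(d√n − 1.96√(2p̄(1 − p̄))) / √(p₀(1 − p₀) + p₁(1 − p₁))}, where p₀ and p₁ are the control and aspiration rates, d = p₁ − p₀ and p̄ is their mean.

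| Assumed control rate | Detectable rate, n = 106 | Detectable rate, n = 125 |
|---|---|---|
| 2% | 11.7% | 10.6% |
| 5% | 17.0% | 15.8% |
| 10% | 24.5% | about 23% |

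Only large excesses would be detected. If no event of a given kind were seen among 106 patients, the one-sided 95% upper bound for its rate in that arm would be 1 − 0.05^(1/106) = 2.8%.

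**The case against.** Four points can be made for the plan.

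1. **Section 3.9 does compare some harm.** Retained hemothorax and empyema are complications, and surgery, reoperation and readmission often follow from complications. A reader might infer that no complication is compared, or that the trial cannot say whether aspiration adds harm. The list does not support either reading, because an excess of these events under aspiration would be visible.

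2. **The first objective is not limited to one arm.** Tube malposition, or bleeding and air leak related to the tube, belong there. At an assumed 10% background rate, 0.10 × 106 = 10.6 operated patients would have such an event with no effect of aspiration. A reader might conclude that all of them would be counted as aspiration complications. Nothing in the documents says they would be filed that way.

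3. **Unequal recording is not shown.** Section 3.8 describes one form, completed by the treating professionals from arrival, with no distinction by arm. The form is not reproduced, so it cannot be said that control-arm events go unrecorded or that a common checklist is missing.

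4. **Some events belong to one arm.** Complications that only the cannula can cause have no control counterpart, and describing them in the operated group is reasonable.

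All four stand, and they narrow the point without removing it. Events with more than one possible cause still need a control rate, and section 3.9 does not ask for one. Sedation is the clearest case. The sedation exclusion in section 3.5 applies to all patients, yet 2.2 mentions sedation only for the operated group, and the documents do not say whether controls are sedated. If they are, a comparator exists and is unused. If they are not, sedation is part of what aspiration adds, and events such as desaturation still need the control rate.

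**Conclusion.** The point holds as a mismatch between objectives and analysis. Section 2.2 seeks aspiration and sedation complications in the operated group, and section 3.9 compares neither these nor the other tube complications, apart from empyema. Procedural or sedation harm that does not appear as one of the outcomes listed in 3.9 would have no between-arm estimate.

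The size of any such harm cannot be stated, because the documents give no rates. What can be stated is the information forgone: at an assumed 10% rate, a risk difference with a half-width of about 7 to 8 points at 125 or 106 per arm. This would not settle rare harms, but it would be a randomised estimate where the plan now has none. It is a cheap improvement and does not affect the validity of the main comparison on clotted hemothorax.

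**What to change.** - **Section 2.2:** reword the second objective to compare complications of the pleural procedure and of sedation between the randomised arms. Events that only the cannula can cause may still be described for the operated group.
- **Section 3.8:** define the complications, and put the same checklist on the existing form for both arms over the same period. If the form already has this, say so. State whether control patients are sedated, so that the sedation items can be interpreted.
- **Section 3.9:** add the number and percentage of patients with any complication, and with each listed one, by randomised arm. Give the risk difference with its 95% confidence interval, and use an exact test where counts are small.

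The cost is wording, at most one checklist, one table and slightly more form-filling for control patients. The sample size, treatment and main question do not change. The report should say that precision is limited and that finding no significant difference does not show equal safety.

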### 3 METHODOLOGY

#### 3.1 Type of study:

Prospective, randomized, controled

#### 3.2 Target population:

Pablo Tobon Uribe Hospital (HPTU) patients

#### 3.3 Study population:

Patients over 18 years of age, with blunt and / or penetrating chest trauma, who are admitted to the HPTU ER, with documented hemothorax or hemoneumothorax and comply the inclusion and exclusion criteria

#### 3.4 Inclusion criteria:

Patients with a diagnosis of traumatic hemothorax of any origin, who have criteria for performing a closed thoracostomy as part of their treatment, will be included in the study

#### 3.5 Exclusion criteria:

- Any previous surgical procedure in the hemithorax to intervene
- Hemodynamic instability requiring urgent thoracotomy in the patient
- Drawing blood from the chest cavity that defines massive hemothorax
- Outflow of intestinal / gastric material, bile, chyle or saliva from the hemithorax at the time of performing a closed thoracostomy
- Patient who entered the service with a closed thoracostomy performed

- Need for major surgical intervention in the injured hemithorax to perform repair of an intrathoracic injury.

- Contraindication for sedation and moderate analgesia in the emergency department: those patients at risk of complications such as craniofacial malformations, predictors of difficult airways, serious or decompensated heart disease, lung, liver, kidney or central nervous system diseases, morbid obesity, sleep apnea, pregnant women

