### 3.7.2 Diagnostic bias:

Chest x-ray read by surgeon and urgentologist on duty. A nomogram will be used to measure the amount of blood in the chest and define if it requires a closed thoracostomy

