### 3.7.3 Randomization:

Randomization was made in EPIDAT4.0, defining the sequence of the intervention and non-intervention groups based on the consecutive admission of the patient to the study.

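### Massive hemothorax is excluded on blood drawn, which the randomized aspiration itself draws, with no stated allocation time and no analysis set

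*Combined protocol and SAP*

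**What the plan says.** The randomized intervention is aspiration with a Yankauer cannula "through the insertion hole of the thoracostomy tube prior to its introduction by the surgeon" (section 2.1). Section 1 gives its purpose as emptying the chest of the whole hemothorax before the tube is placed.

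Three exclusions in section 3.5 can come to light during or after the procedure:

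- "Drawing blood from the chest cavity that defines massive hemothorax", with no volume, time window or measuring method.
- "Need for major surgical intervention in the injured hemithorax to perform repair of an intrathoracic injury", with no time limit.
- "Outflow of intestinal / gastric material, bile, chyle or saliva from the hemithorax at the time of performing a closed thoracostomy".

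On the order of events, section 3.3 describes the study population as patients "with documented hemothorax or hemoneumothorax and comply the inclusion and exclusion criteria". Section 3.7.3 describes randomization as "defining the sequence of the intervention and non-intervention groups based on the consecutive admission of the patient to the study". Neither says when the arm becomes known relative to opening the chest, aspiration or the exclusion checks. Section 3.7.2 does provide a measure made before the procedure, "A nomogram will be used to measure the amount of blood in the chest and define if it requires a closed thoracostomy", but it serves the thoracostomy decision and not the massive-hemothorax exclusion.

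Section 3.9 names the outcomes, need for surgery and reoperation among them, and a chi-square test. It does not say who is analysed. Section 3.6 plans 125 per arm, "calculating a loss of patients of 15% in each arm", without saying whether exclusions count as loss.

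**The concern.** An exclusion is harmless to the comparison if it is settled before the arm is known, or on facts the arm cannot influence. The massive-hemothorax rule is secured on neither count. It depends on the amount of blood drawn, and drawing blood is what the intervention does. In the aspiration arm the blood is first drawn by the cannula; in the control arm it drains through the tube. The same patient could therefore be counted differently according to arm.

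If such patients are removed after allocation, the arms can lose different numbers or different types of patient, and the test no longer compares the groups that were randomized. If those removed have above-average clot risk and more of them leave the aspiration arm, a benefit appears where none exists. If their risk is below average, or more leave the control arm, the error runs the other way. An equal 15% loss allowance protects the sample size but not against this.

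The surgery rule raises a related ambiguity: a patient operated on after allocation could be read as an exclusion under section 3.5 or as an outcome under section 3.9.

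**Working it through.** **1. When each criterion can be known**

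| Criterion (section 3.5) | Earliest point it can be judged | Can the arm affect it? |
|---|---|---|
| Massive hemothorax by blood drawn | When the chest is drained: by cannula in the aspiration arm, by tube in control | Yes, by inference from sections 1 and 2.1 |
| Major repair surgery | No time limit given | Can be judged with the arm known; overlaps an outcome in section 3.9 |
| Abnormal outflow | At the thoracostomy, possibly on opening the chest | Lesser concern: may be visible before the arms diverge |

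For the first criterion to precede allocation, it would have to be checked between opening the chest and aspirating. No such step is described.

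**2. The plan's own sample size**

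Inputs from section 3.6: 16.7% versus 5%, 15% loss. Two-sided alpha 0.05 and 80% power are assumed, since neither is stated. With unpooled variance:

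n = (1.960 + 0.842)² × (0.167×0.833 + 0.05×0.95) / 0.117² = 7.849 × 0.1866 / 0.01369 = 107 per arm.

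Then 107/0.85 = 126, or 107 × 1.15 = 124. The planned 125 is reproduced closely. Other variants also come near it, so alpha and power cannot be recovered uniquely. After 15% loss, 125 × 0.85 = 106 per arm.

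**3. What differential exclusion could do**

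Assumptions not in the documents: a share f is excluded from an arm, and the excluded have clot risk r. There is no true effect, overall risk is 16.7%, and there are 106 per arm before exclusion. The remaining risk is (0.167 − f×r)/(1 − f), with n = 106×(1 − f), rounded. False benefit is the probability that the uncorrected chi-square test (two-sided 0.05, exact binomial enumeration) is significant with aspiration lower.

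Worked line, f = 10% versus 5%, r = 50%: aspiration (0.167 − 0.050)/0.90 = 13.0%, n = 95; control (0.167 − 0.025)/0.95 = 14.95%, n = 101; apparent difference 1.9 points.

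| Excluded (aspiration vs control) | r | Apparent benefit, points | False benefit | False harm |
|---|---|---|---|---|
| None | – | 0 | 2.5% | 2.5% |
| 10% vs 10%, same type | 5–50% | 0 | 2.5% | 2.5% |
| 10% vs 5% | 5% | −0.7 | 1.8% | 3.4% |
| 10% vs 5% | 30% | 0.8 | 3.5% | 1.8% |
| 10% vs 5% | 50% | 1.9 | 5.7% | 1.0% |
| 10% vs 0 (extreme) | 5% | −1.3 | 1.4% | 4.4% |
| 10% vs 0 (extreme) | 30% | 1.5 | 4.7% | 1.3% |
| 10% vs 0 (extreme) | 50% | 3.7 | 11.1% | 0.4% |

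The planned difference is 16.7 − 5 = 11.7 points. In the last row the excluded hold 0.10×0.50/0.167 = 30% of that arm's events. If r equals the average 16.7%, there is no bias. If control loses more, the results mirror.

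**4. What keeping these patients could cost**

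Base power at 106 per arm, 16.7% versus 5%, is 81%. Suppose those rates hold in the other patients and the retained share f has risk r in both arms. The arm risks become (1 − f)×0.167 + f×r and (1 − f)×0.05 + f×r.

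- f = 5%, n = 106: power 78%, 73% and 70% at r = 5%, 30% and 50%. It is about 2 points higher if n rises to 106/0.95 = 112 because these patients come out of the 15% allowance.
- f = 10%, n = 106: 75%, 65% and 59%. It is about 4 points higher at 106/0.90 = 118.

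If instead 16.7% is the overall control risk and the planned relative reduction applies only to the rest, power at n = 106 is 64–80% (5% retained) and 45–78% (10% retained). Excluding them equally from both arms would give 74–81% and 64–80%. If the retained share the relative benefit, power at n = 106 is 78–89%.

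**The case against.** The strongest reply is that eligibility comes first. Sections 3.3 and 3.7.3 can be read together as admitting to the study only patients who already meet all criteria and allocating them afterwards; on that reading no bias follows. This stands as a possible intention. It does not fit the massive-hemothorax rule as worded, because blood drawn is not known before the chest is drained, and one companion exclusion is explicitly observed during the thoracostomy.

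Four further objections have weight:

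- That aspiration moves patients across the definition of massive hemothorax is an inference. Controls also drain blood, and the definition and time window are not given. The point is that the arm can affect the count, not that it does.
- The surgery limb is weaker than it may look. Listing need for surgery and reoperation as outcomes suggests that at least some surgery after enrolment is counted rather than used to remove patients. Section 3.9 does not separate repair from evacuation surgery, so the passages need reconciling; they do not show that operated patients would be dropped.
- All exclusion shares and risks are assumed. Adding both tails, total error for 10% versus 5% is 0.0349 + 0.0176 = 0.0525 at r = 30% and 0.0573 + 0.0097 = 0.0670 at r = 50%, modest against 0.05. The 11.1% figure needs one-sided loss and about three times the average risk together.
- Keeping these patients can cost considerable power: 45% against 64% under equal exclusion in the least favourable case shown. But equal exclusion is exactly what a rule applied after allocation cannot guarantee.

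A reader might infer that the trial drops patients differentially, or is biased in favour of aspiration. The documents support neither.

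**Conclusion.** The concern holds in a conditional form. As written, a stated exclusion rests on information that the randomized procedure generates. The plan neither places allocation after that check nor defines an analysis set that would keep the patients it removes. This goes beyond missing detail, because following the rule literally can break the randomized comparison, and that cannot be restored afterwards without outcome data on those removed.

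Size and direction are unknown. Over the assumed range the chance of a false benefit lies between 1.4% and 11.1% against 2.5% nominal, with apparent differences from 1.3 points against aspiration to 3.7 points in its favour. These figures illustrate sensitivity and do not estimate what will happen. The repair-surgery overlap between sections 3.5 and 3.9 must be reconciled, and abnormal outflow is a lesser issue. This should be fixed; confidence is medium, because the intended sequence may be sound and simply not written down.

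**What to change.** In sections 3.5 and 3.7.3:

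- State when allocation is revealed relative to each exclusion check.
- Apply exclusions only on information available before allocation.

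In section 3.9:

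- Define the primary analysis as all randomized patients in their allocated arm.
- Report massive output, abnormal outflow and repair surgery found after allocation by arm.
- Reconcile repair surgery as an exclusion with need for surgery as an outcome, and prespecify how clotted hemothorax is scored after repair surgery.
- Use the analysis without these patients only as a sensitivity analysis.

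No clinical threshold or change of care is proposed.

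Most of this is wording and one scoring rule, but there are two real costs. First, outcome follow-up must continue for these patients. Section 3.8 starts the form at emergency entry but does not promise outcomes for anyone excluded. Second, power may fall if they do not benefit, as in step 4 of the working; if they share the benefit, little or nothing is lost. Revealing allocation as late as feasible would shrink the retained group. That may not be possible if sedation differs by arm: section 2.2 links sedation to aspiration in the operated group, and the plan does not say whether controls are sedated.
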